Subjects eligible for the study include both males and females, 28 days to < 18 years of age, with congenital or acquired heart disease who are at risk for thrombus formation that can result in vascular, intracardiac or coronary artery thrombosis, or embolization to other organs or tissue, and who require chronic anticoagulation for thromboprophylaxis as determined by the treating physician with guidance from major current guidelines (ACCP 2012 guideline). To be eligible for the study, subjects under age 2 years should be expected to require anticoagulation for a minimum of 1 month; whereas subjects ≥ 2 years of age should be expected to require anticoagulation for a minimum of 6 months, although the full treatment duration of 12 months is most desirable. Subjects who are expected to be chronically anticoagulated (> 1 year), should have a study treatment duration of 12 months. Eligible subjects include those who newly start anticoagulants and those who are currently on VKA or LMWH for thromboprophylaxis. The investigator is responsible for working with the treatment team to determine if a subject meets the criteria for thromboprophylaxis per the current ACCP guideline. The reasons the subject is receiving prophylaxis will be documented on the eCRF.

Three age groups will be included in the study: 28 days to < 2 years, 2 years to < 12 years, and 12 years to < 18 years. Every effort will be made to ensure appropriate representation for each of the age groups. The neonate cohort will be removed from the study population [redacted] upon approval of this revised protocol.

[redacted] Recruitment started in January 2017 for children of ages ≥ 2 to < 18 years and was extended to children ages 3 months to < 2 years in December 2017. Recruitment opened to children 28 days to < 3 months old in February 2020.

Key Inclusion Criteria:

1. Males and females, 28 days to < 18 years of age
2. Congenital or acquired heart diseases requiring chronic anticoagulation for thromboprophylaxis (e.g., single ventricle physiology including all 3 stages of palliation, dilated cardiomyopathy, Kawasaki disease with coronary aneurysms, and pulmonary hypertension).
Note: subjects with previous history of thromboembolic events greater than 6 months prior to enrollment are eligible, provided there is evidence (by previously obtained clinical imaging data) for thrombus stability or resolution.

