During the **Treatment Period**, in-person study visits will occur at 2 weeks \pm 3 days, 3 months \pm 2 weeks, 6 months \pm 2 weeks, and 12 months \pm 2 weeks. Subjects who are < 2 years of age will have a mandatory in-person visit at 9 months \pm 2 weeks to include weight measurement, dose adjustment (if necessary) reporting adverse events, and assessing medication adherence. Subjects who are \geq 2 years of age have the option of an in-person or a phone call visit at 9 months \pm 2 weeks. Subjects aged 28 days to < 3 months at the time of randomization will have an office visit at 6 weeks \pm 3 days for assessment of body weight in order to adjust the dose of study medication

(if necessary). The phone visit will monitor adverse events and medication adherence. The timing of these study visits will coincide as much as possible with standard-of-care visits for these pediatric subjects. Visits will consist of clinical evaluation of thromboembolic events, bleeding events, reporting AEs, therapeutic monitoring (INR for VKA or anti-Xa activity for LMWH), monitoring medication adherence, safety laboratory studies (CBC, ALT, AST, total and conjugated bilirubin), serum or urine pregnancy test for WOCBP and concomitant therapy assessment for all enrolled subjects. Subjects on VKA or LMWH may have additional visits as needed for adjustment of their dose and monitoring at the discretion of the investigator and/or treating physician. PK/PD samples will be drawn at Day 1, Week 2, Month 3, and Month 6. No PK/PD samples will be drawn at the 6 month visit for subjects < 3 months of age. [REDACTED] PK/PD [REDACTED] samples will be analyzed at a central core laboratory. Safety labs will be analyzed locally.

The subject’s weight will be measured at the 3, 6 (subject 28 days to < 3 months of age), 9, and 12 month visit. A 6 week visit is mandatory for subjects < 3 months of age at randomization. A 9 month office visit is mandatory for subjects < 2 years of age or can be either an office visit or phone visit for subjects ≥ 1 year of age, and the apixaban dose should be adjusted based on body weight changes according to the dosing guidance document that will be provided to each site.

[figure not shown]

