3.3 Study Population

Subjects eligible for the study include both males and females, 28 days to < 18 years of age, weighing ≥ 3 kg, and with congenital or acquired heart disease who are at risk for clot formation that can result in vascular, intracardiac or coronary artery thrombosis, or embolization to other

organs or tissues, and who require chronic anticoagulation for thromboprophylaxis as determined by the treating physician with guidance from major current guidelines [ACCP (American College of Chest Physicians) 2012 guideline]. To be eligible for the study, subjects under age 2 years should be expected to require anticoagulation for a minimum of 1 month; whereas subjects ≥ 2 years of age should be expected to require anticoagulation for a minimum of 6 months, although the full treatment duration of 12 months is most desirable. Eligible subjects include those who newly start anticoagulants and those who are currently on VKA or LMWH for thromboprophylaxis. The investigator is responsible for working with the treating team to determine if a subject meets the criteria for thromboprophylaxis per current ACCP guideline. Reasons for why the subject is receiving prophylaxis will be documented on the electronic case report form (eCRF).

Three age groups will be included in the study: 28 days to < 2 years, 2 years to < 12 years, and 12 years to < 18 years.

For entry into the study, the following criteria MUST be met.

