Apixaban doses can be administered by mouth (PO) or via a NGT or GT approximately 12 hours apart, followed with or without food. The oral solution should be administered with the appropriate dosing syringe provided by the Sponsor. The apixaban 5 mg tablet can be crushed and suspended in water or 5% dextrose in water (D5W) or apple juice or can be mixed with applesauce and promptly administered orally. Alternatively, apixaban 5 mg tablets can be crushed and suspended in 60 mL of water or D5W and promptly delivered through a NGT. The apixaban 0.5 mg tablets can be mixed with applesauce or can be dissolved in water, apple juice, or formula and promptly administered orally or via NGT/GT. Apixaban should not be administered through NJT/post-pyloric feeding tubes due to decreased absorption. The apixaban 0.1 mg capsules will need to be opened and dissolved in infant formula or breast milk and promptly administered orally or via NGT/GT.

The subject's weight will be measured at the 6 week (subjects < 3 months only), 3, 6, 9 (subjects < 2 years only), and 12 month office visits, and the apixaban dose should be adjusted based on body weight changes according to the dosing guidance document that will be provided separately. Apixaban can be administered by mouth (PO) or via a NGT or G-tube, beginning when subjects are able to tolerate enteral intake. Subjects 28 days to < 3 months must be able to tolerate oral/NGT/GT feeds for at least 5 days prior to randomization.

Apixaban should not be administered through NJT/post-pyloric feeding tubes due to decreased absorption. For post-operative subjects, study medication should begin when subjects are able to tolerate enteral intake after the procedure when adequate hemostasis has been established (e.g., after removal of surgical drains, lines, and wires, etc.), but no sooner than 24 hours after the procedure and no more than 10 days after surgery. Chest tubes and other instrumentation that could cause bleeding should be removed prior to initiation of therapy. Bridging strategies with UFH are permitted in the interim, per local institutional practices. The oral solution should be administered with the appropriate dosing syringe provided by the Sponsor.

It is recommended that subjects take their study medication at the same time each day.

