| Chromogenic FX assay Apixaban subjects only | | X | Day 1 Prior to 1st dose, 4 hr (3- 8 hr) post dose Each sample will be approximately 1.4 ml of blood For those subjects on warfarin who are randomized to apixaban and have to wait for their INRs to be within range before starting apixaban, the Day 1 post dose 4 hr (3-8 hr) sample should be postponed and only be done 3-8 hr after the subject has taken their first dose of apixaban |
| | | | |
| Efficacy Assessments | | | |
| QOL assessment | | X | PedsQL and KIDCLOT QOL instruments to be administered to English speaking subjects who have been previously taking an anticoagulant. Subjects newly taking anticoagulants will be given the PedsQL only at this visit. The QOL instruments needs to be completed at the time of the visit |
| Study Drug Supplies | | | |
| Enroll via IWRS | X | | |
| Randomize via IWRS | | X | Subjects can be enrolled and randomized during the same visit. |
| Dispense Study Drug | | X | Apixaban, warfarin and enoxaparin will be supplied by BMS or warfarin and |

Table 5.1-1: Screening Procedural Outline (CV185362)

| Procedure | Consent/ Screening Visit Day -21 to 1 | Randomization Visit Day 1 | Notes |
|------------------------|--|--|--|
| | | | LMWH will be sourced locally by the study site. Study drug diaries will be used to record study drug administration. |
| Dispense Patient Diary | | X | Patient diary will be used to collect dose, date, and time of when study medication is administered to the subject |

Table 5.1-2: Study Procedural Outline (CV185362)

| Procedure | During Treatment ^d | | | | | End of Treatment | Follow-up | Notes |
|-----------------------------------|-------------------------------|---|-------------------|--------------------------------|-------------------|---|---|--|
| | Week 2 ± 3 days | Week 6 ± 3 days (only subjects < 3 months at time of randomization) | Month 3 ± 2 weeks | Month 6 ± 2 weeks ^e | Month 9 ± 2 weeks | Month 12 ± 2 weeks or early drug discontinuation | Month 14 ± 2 weeks (or 2 months after the end of anticoagulation) | |
| Concomitant Medication Assessment | X | | X | X | X | X | X | Subjects ≥ 2 years of age have the option of an in-person or a phone call visit at 9 months ± 2 weeks. Subjects < 2 years of age are required to have an office visit |

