| Body Weight | | X | X | X | X | X | | Apixaban dose should be adjusted based on body weight changes according to dosing guidance document provided to the site. Subjects ≥ 2 years of age have the option of an in-person or a phone call visit at 9 months ± 2 weeks. Body weight will only be taken at the office visits |
| Safety Assessments | | | | | | | | |
| Targeted Physical Examination | X | | X | X | | X | | Includes organ systems pertinent to the subject's signs, symptoms, or adverse events, e.g., assessment of signs of bleeding |
| Vital Signs | X | | X | X | | X | | Heart Rate, BP, respiratory rate and temperature |
| Serious Adverse Event Assessment | X | X | X | X | X | X | X | Collection of SAEs begins after signed consent. Subjects ≥ 2 years of age have the option of an in-person or a phone call visit at 9 months ± 2 weeks. The 6 week visit is only for those subjects < 3 months. |
| Adverse Events Assessment | X | X | X | X | X | X | X | Collection of non-serious AEs begins after randomization. Subjects ≥ 2 years of age have the option of an in-person or a phone call visit at 9 months ± 2 weeks. The 6 week |

Table 5.1-2: Study Procedural Outline (CV185362)

| Procedure | During Treatment ^d | | | | | End of Treatment | Follow-up | Notes |
|---|-------------------------------|---|-------------------|--------------------------------|-------------------|---|---|--|
| | Week 2 ± 3 days | Week 6 ± 3 days (only subjects < 3 months at time of randomization) | Month 3 ± 2 weeks | Month 6 ± 2 weeks ^e | Month 9 ± 2 weeks | Month 12 ± 2 weeks or early drug discontinuation | Month 14 ± 2 weeks (or 2 months after the end of anticoagulation) | |
| | | | | | | | | visit is only for those subjects < 3 months. |
| Laboratory Tests ^a | X | | X | X | | X | | CBC, ALT, AST, total and conjugated bilirubin for all subjects. INR for subjects receiving VKA or anti-Xa activity for subjects receiving LMWH as per SOC |
| Pregnancy Test WOCBP only | X | | X | X | | X | | |
| | | | | | | | | |
| PK, PD [REDACTED] | | | | | | | | |
| PK Sampling Apixaban patients only ^b | X | | X | X | | | | Week 2: Pre-dose sample Month 3: 2 ± 1 hr post dose sample Month 6: Pre-dose sample For those children < 3 months of age at randomization, blood samples will only be taken at Day 1, Week 2, and Month 3. A dried blood spot technique can be used for PK sampling in children < 3 months of age at randomization |

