| Dispense Study Drug | | X* | X | X | X* | | | *For subjects who will have a Week 6 or Month 9 office visit, study medication will be dispensed. Dose will be adjusted for weight gain if necessary. Study drug diaries will be used to record study drug administration |
| Collect Patient Diary | | | X | X | X | X | | If subject is there for an office visit, verify patient diary completion, study drug compliance, and dispense patient diary back to subject |
| End taking Study Drug | | | | | | X | | The study medication will start on Day 1 and continue up to 12 months or until the need for anticoagulant is resolved, whichever is shorter. |

^a INR levels for subjects receiving VKA and anti-Xa levels for subjects receiving LMWH as part of SOC will also be collected between visits per SOC and recorded at each visit. Those INRs collected between visits via a home monitoring device will be logged in diaries and recorded at the subsequent visit.

^b For subjects who discontinue before the month 6 visit, blood samples will be taken at the end of the treatment discontinuation + 2 weeks.

^d Week 6 visit only for those subjects < 3 months of age at the time of randomization

e No PK/FXa/chromogenic samples taken at Month 6 for children < 3 months

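### Minor: apixaban infants aged 3 months or more and under 6 kg have no scheduled weight or dispensing between Day 1 and Month 3, so the weight-tier dose may lag growth for some weeks

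*Combined protocol and SAP*

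**What the plan says.** Table 4.5-1 sets the apixaban dose by weight alone: 0.2 mg twice daily at 3 to under 4 kg, 0.3 mg at 4 to under 5 kg, 0.5 mg at 5 to under 6 kg, and 1 mg at 6 to under 9 kg.

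Section 3.3 admits children "28 days to < 18 years of age, weighing ≥ 3 kg". The only weight exclusion in Section 3.3.2 is below 3 kg, so an infant of 3 months or more who weighs 3 to under 6 kg is eligible.

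On weighing, Section 4.5 has this rule: "weight will be measured at the 6 week (subjects < 3 months only), 3, 6, 9 (subjects < 2 years only), and 12 month". Section 3.1 restricts the 6-week weight in the same way, worded as a recommendation. In Table 5.1-2 that column is headed "Week 6 ± 3 days (only subjects < 3 months at time of randomization". The first visit column is Week 2, and it is empty in two rows:

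- body weight: "Body Weight | | X | X | X | X | X"
- dispensing: "Dispense Study Drug | | X* | X | X | X"

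The dispensing note adds: "For subjects who will have a Week 6 or Month 9 office visit, study medication will be dispensed".

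The Synopsis (Study Assessments, Treatment Period) differs. Its sentence reads: "weight will be measured at the 3, 6 (subject 28 days to < 3 months of age), 9, and 12 month visit". That limits the Month 6 weight to the youngest group. Sections 3.1 and 4.5 and Table 5.1-2 do not.

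**The concern.** The Week 6 visit exists so that a growing infant can be weighed and the dose adjusted, yet it is assigned by age while the dose is assigned by weight. An infant just over 3 months old in a 1-kg-wide tier can outgrow that tier as readily as a younger one, but is not due to be weighed or resupplied until Month 3. At stake is agreement between the dose given and the plan's own dose table, in the apixaban arm, for some weeks and in what may be very few infants.

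**Working it through.** **Inputs from the protocol.** A month is 30 days (Section 3.1). Month 3 is day 90 ± 14, so day 76 to 104. Doses are from Table 4.5-1. Weight is taken at screening and Day 1 (Table 5.1-1).

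**Gap.** For an infant of 3 months or more, the next scheduled weight and dispensing after Day 1 is Month 3: 90 days, range 76 to 104.

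**Dose held against dose due after passing one limit.**
- 4 kg: 0.2/0.3 = 67%
- 5 kg: 0.3/0.5 = 60%
- 6 kg: 0.5/1 = 50%

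**How much of this is the table's own step.** Dose per kg barely moves at the limit: 0.5/5.9 = 0.085 mg/kg and 0.5/6.0 = 0.083 mg/kg. An infant of 5.5 kg gaining an assumed 0.3 kg per 30 days weighs 5.5 + 3 × 0.3 = 6.4 kg at day 90. On an unchanged 0.5 mg, dose per kg falls from 0.5/5.5 = 0.091 to 0.5/6.4 = 0.078, or 14%. The tabled 1 mg would give 1/6.4 = 0.156. Within the 6 to under 9 kg tier the table accepts a fall from 1/6 = 0.167 to 1/9 = 0.111, or 33%.

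**Time below the tabled dose.** The documents give no growth rate, start-weight spread or number of such infants. Assumed: linear gain of g kg per 30 days (r = g/30 per day), start weights even over 5 to under 6 kg, and uninterrupted dosing. Count the days 0 to T − 1 on which the dose held is below the Table 4.5-1 dose.

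- No check, rT ≤ 1: mean days = r·T(T − 1)/2. At g = 0.2 and T = 90: (0.2/30) × 90 × 89/2 = 26.7.
- No check, rT > 1: T − 1/(2r) − 1/2. At g = 0.5: 90 − 30 − 0.5 = 59.5.
- Weight at day 14 only (slower growth): r(14 × 13 + 76 × 75)/2 = 2941r. At g = 0.2: 19.6.
- Weights at days 14 and 42 (slower growth): r(14 × 13 + 28 × 27 + 48 × 47)/2 = 1597r. At g = 0.2: 10.6.

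The checked figures at g = 0.5 and 0.7 come from the same day count run directly.

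| g (kg per 30 days) | Share passing 6 kg by day 90 | No check | Week 2 weight | Weeks 2 and 6 |
|---|---|---|---|---|
| 0.1 | 30% | 13.35 | 9.8 (−27%) | 5.3 (−60%) |
| 0.2 | 60% | 26.7 | 19.6 (−27%) | 10.6 (−60%) |
| 0.3 | 90% | 40.05 | 29.4 (−27%) | 16.0 (−60%) |
| 0.5 | 100% | 59.5 | 41.8 (−30%) | 19.4 (−67%) |
| 0.7 | 100% | 68.1 | 43.2 (−37%) | 11.9 (−83%) |

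**Sensitivity, no check.**
- Month 3 at day 76: 9.5 to 54.1 days. At day 104: about 17.9 to 82.1 days.
- Treatment ending at day 30: 1.45 to 10.15 days. This case matters because "subjects under age 2 years should be expected to require anticoagulation for a minimum of 1 month".
- Starts in 4 to under 5 kg: same unchecked means, and same savings up to g = 0.3. At g = 0.5 and 0.7 the savings are smaller, because a second limit may be passed. With Week 2 alone, 47.0 and 56.2 days remain (1 − 47.0/59.5 = 21%; 1 − 56.2/68.1 = 17%). With both weights, 26.6 and 37.0 remain (55% and 46%).

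**The case against.** The strongest reply is that the operative rule is elsewhere. Sections 3.1 and 4.5 refer dose adjustment to a separate dosing guidance document, which may already allow changes between visits. Nothing in the protocol forbids an interim weight or resupply, Week 2 is in person, and visits are meant to coincide with clinical care. This stands as a limit on the consequence. The gap in the schedule itself remains.

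The age cut also has some support. Section 1.4 reports weight-normalized clearance as constant from 3 months to 18 years, with a trend to age dependence below 3 months. That makes closer follow-up of the youngest defensible. It does not fully answer the point, because the stated purpose of the Week 6 visit is weight.

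The 6 kg cut-off is partly a choice. An infant of 8.8 kg passing 9 kg has the same gap, and infants also go about 90 days without a scheduled weight from Month 3 to Month 6. The tiers below 6 kg are 1 kg wide and the dose doubles at 6 kg, which is why they come first. But the Month 3 to 6 interval weakens the case for requiring an extra visit. The group may also be nearly empty: Section 1.1.2 shows that enrolment from 3 months was earlier limited to children over 6 kg.

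A reader might infer that these infants are under-anticoagulated at half dose, or that the PK results or the bleeding and thrombosis comparisons are compromised. The documents do not support that. The 50% is a ratio of tabled doses, dose per kg moves far less, and no exposure or outcome effect can be derived from what is given.

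**Conclusion.** The point holds as a minor, cheap improvement to the dosing schedule. The absence of a scheduled weight or dispensing before Month 3 is certain from Sections 3.1 and 4.5 and Table 5.1-2. That a given infant stays on the lower tier's dose is only possible, and depends on the unseen dosing guidance and on routine clinic weights. The size, roughly 13 to 68 mean days below the tabled dose in the first 90, rests wholly on the assumed growth and start weights, and shrinks to about 1 to 10 days if treatment lasts 30 days. The trial's validity is not in question. The Synopsis sentence on the Month 6 weight is a separate wording inconsistency, possibly a slip for the 6-week visit.

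**What to change.** In Sections 3.1 and 4.5 and Table 5.1-2:

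1. Add body weight at the existing Week 2 visit for subjects under 6 kg, with dispensing if the tier has changed.
2. State that any weight in a new tier, from whatever visit, triggers a dose change and resupply without waiting for the next scheduled visit.
3. Optionally, extend the Week 6 weigh-and-adjust visit to every subject under 6 kg at randomization. The longest scheduled gap then falls to 90 − 42 = 48 days, against 90 − 14 = 76 days with the Week 2 weight alone.
4. Align the Synopsis weight sentence with Section 4.5.

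Items 1, 2 and 4 cost almost nothing beyond an occasional resupply. Item 3 costs one short extra visit for a few infants. The step at 6 kg uses the same 0.5 mg tablets, two instead of one; the step at 5 kg needs a change from capsules to tablets. The trade-off is an earlier step up in dose. If the dosing guidance already provides for changes between visits, only the schedule wording needs aligning.

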4.5.1 Missed Dose and Vomiting/Regurgitation

If a dose of apixaban is missed the subject should take the study medication immediately and then continue with twice daily administration as before. A double dose should not be taken to make up for a missed dose. Subjects may take a missed dose up to 6 hours after the normal dosing time. If it is greater than 6 hours from the normal dosing time, the missed dose should not be taken. Instead, the next scheduled dose should be taken at its normal time.

If a subject vomits or regurgitates within 30 minutes after ingestion of the study drug, re-dosing is allowed; but the study drug can be given again one time only. If the subject vomits/regurgitates more than 30 minutes after study drug ingestion, no additional study drug should be taken, and the subject should resume study drug ingestion according to the usual schedule.

4.5.2 Temporary Treatment Interruptions

During the course of the study, situations might occur in which the investigator considers a temporary interruption of study drug treatment necessary. For example, a scheduled surgical procedure, perioperative use of CPB, or elevated liver function tests. The treating physician should be informed about recommendations for timing and dosage of study drug (apixaban or active comparator) administration in such circumstances.

For treatment interruptions ≥ 48 consecutive hours, the period of interruption should be noted and the investigator should document on the CRF the time and date of discontinuation and restart of therapy, as well as the reason for interruption and measures taken to correct the event. An AE should be reported if applicable.

Guidance on temporary dose interruptions for selected events are described below. For an individual subject, dose interruptions and treatment discontinuation may be more or less conservative than indicated below based on the clinical judgment of the investigator. Note that discontinuation of subjects from treatment is addressed in [Section 3.5](#).

Elective Procedure or Surgery

Apixaban: The effective half-life of apixaban when administered twice daily is approximately 12 hours, and it is expected that most of the anticoagulation effect will be gone within 24 hours after the last dose of the drug. Apixaban must be stopped for a sufficient period of time (e.g., at least 24 hours if the risk of bleeding is low and at least 48 hours if the risk of bleeding is moderate or high) prior to the procedure to minimize the risk of anticoagulant-related bleeding. The treating physician should be made aware of the time and dosage of apixaban administration and be informed that routine coagulation tests such as INR and aPTT are relatively insensitive measures of anticoagulation activity and are unsuitable for monitoring the anticoagulation effect of apixaban. The subject will re-start study medication once hemostasis is secure (e.g., after removal of surgical drains, lines, and wires, etc.), and when, in the opinion of the investigator, it is safe to do so, at such time as a patient would otherwise be transitioned to VKA or LMWH per local institutional standards, but no earlier than 24 hours and no later than 10 days after the procedure/surgery. Bridging strategies with UFH are permitted in the interim, per local institutional practices.

Elevated Liver Function Tests (applies to both the apixaban and comparator groups)

If at any time during the treatment period a subject's liver function test (LFT) results show:

An isolated elevation of either $ALT/AST \geq 5 \times ULN$ AND/OR a direct (conjugated) bilirubin $> 2 \times ULN$, obtain the following laboratories: ALT, AST, total bilirubin, direct bilirubin, alkaline phosphatase, GGT, CK as soon as possible (i.e. within 3 days).

If the repeat tests indicate:

- 1) ALT/AST $< 5 \times$ ULN and direct (conjugated) bilirubin $\leq 2 \times$ ULN, study medication may continue.
- 2) ALT/AST $\geq 5 \times$ ULN AND/OR the conjugated bilirubin is $> 2 \times$ ULN, the **study medication** must be interrupted.

The study medication must be interrupted if:

- Clinical jaundice is present in a subject at any time unless there is an alternative causative factor such as Gilbert or Dubin-Johnson syndrome

OR

- ALT/AST $\geq 5 \times$ ULN on any two consecutive occasions

OR

- Direct (conjugated) bilirubin $> 2 \times$ ULN on any two consecutive occasions.

All subjects with an ALT/AST $\geq 5 \times$ ULN or direct (conjugated) bilirubin $> 2 \times$ ULN will be followed weekly until ALT/AST returns to $< 3 \times$ ULN or to baseline, and direct (conjugated) bilirubin returns to $\leq 1.5 \times$ ULN or to baseline.

If study medication is discontinued due to elevated ALT/AST OR bilirubin, as defined above, inform the BMS Medical Monitor and perform the following:

- INR, aPTT, fibrinogen to assess liver synthetic function
- Abdominal ultrasound, including liver and hepatobiliary system
- Hepatitis screen (anti-HAV, HBsAg, anti-HBc, anti-HBs and anti-HCV).
- Obtain relevant specialist consultation.

